## **3. Concise Summary of Project:**

Hypothesis: Placental/umbilical cord blood can be used to do early onset sepsis evaluation in low birth weight infants.

Objective: To compare placental/umbilical cord blood and blood from the infant in the evaluation of EOS in VLBW infants.

Specific Aim 1: To compare blood culture, CBC and I/T ratio results of blood from the infant and placental/umbilical cord blood (PUCB).

Objective: All VLBW infants receive empirical broad-spectrum antibiotics after collecting blood for CBC, I/T ratio, and blood culture. We will compare the results of PUCB and blood from the infants, especially comparing white cell count, band count, I/T ratio and if the blood culture is positive or negative. If the blood culture is positive, then we will find out if the micro-organism is the same or not.

Specific Aim 2: To evaluate the role of adding IL-6 and CRP in the evaluation of EOS in VLBW infants.

Objective: We will collect 1 mL of PUCB which will be centrifuged at -40C and serum will be stored at -80 degrees. We will use ELISA to measure IL-6 and CRP. A combination of IL-6 and CRP has been shown to be very helpful in the diagnosis of EOS in VLBW infants. We will also calculate sensitivity, specificity, negative predictive and positive predictive values of IL-6 and CRP individually, as well as, a combination of IL-6 and CRP in the diagnosis of EOS in VLBW infants. We will also find out the duration of antibiotics used in all subjects and find out from IL-6 and CRP data if the antibiotic use was warranted. In future, this may be very useful information in deciding antibiotic duration which will help in avoiding side effects of the unnecessary use of broad-spectrum antibiotics. At present, in our NICU, IL-6 and CRP are not part of EOS evaluation in VLBW infants.

Clinical team will be blinded to the PUCB sepsis evaluation results. In the present study, IL-6 and CRP will not be used clinically but only for research purpose to find out if the addition of IL-6 and CRP help in the management of EOS in VLBW infants.

All VLBW infants get CBC done at admission before starting antibiotics as part of EOS work up. After CBC is done, left over blood sample is saved in the hematology laboratory for 24 hours. We will collect the left-over sample and collect serum after centrifugation. The serum will be saved at -800C for future measurement of IL-6 and CRP. We will compare IL-6 and CRP from infant and PUCB.

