#### *Power analysis:*

In order to do a power analysis to determine sample size, an estimate of effect size was based upon the Rashawn et al (30) study which found significant correlations of CRP with other biomarkers.

In G\*Power (31) the following was used:

- Effect size of  $r=.4$
- Alpha=.05
- Power (1-alpha)=.95
- Yielding a sample size of 63

To accomplish this project, a cohort of preterm infants will be recruited from the infants admitted to the NICU at UTMB, Galveston. We routinely admit around 80 infants/year who are <34 weeks' gestation. We expect to recruit about 50 – 60% VLBW infants born in UTMB, Galveston in the current study. Therefore, we hope to recruit our desired sample size (n=63) in about 18 months.

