#### *Clinical Data Collection:*

We will use electronic medical records to collect medical data from mother's antenatal, delivery and post-delivery information and detailed medical information of the infants. Data derived from blood test analysis in placenta/umbilical blood cord and blood from the infants will be used to assess the accuracy of placenta/umbilical blood cord samples. We will also find out specificity, sensitivity, positive and negative predictive values of CBC, I/T ratio, blood culture, CRP and IL-6 in the evaluation of EOS in ELBW infants. All data will be de-identified but the clinical data will be linked to the discarded samples.

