## **13. Potential Benefits:**

There will be no direct benefit to the subjects. But the results of this study may help us to find out if PUCB could be utilized to evaluate EOS in VLBW infants. The results of this study will provide understanding of the utility of PUBC samples to evaluate EOS in VLBW preterm infants. Moreover, this alternative modality of blood analysis could contribute to the prevention of early hemodynamic instability and early blood transfusion in a very high-risk population of VLBW preterm infants. Furthermore, an additional test for sepsis screening as CRP and IL 6, might improve the accuracy for EOS evaluation, and may avoid or prevent unnecessary and prolong antibiotic use in ELBW infants.

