## **14. Biostatistics:**

Statistical analyses will be performed using SPSS 25 for Windows (SPSS Inc., Chicago, IL, USA). Demographic and clinical characteristics will be compared using the non-parametric Mann-Whitney U test, and the results will be presented as medians (range). Categorical variables will be compared using the linear-by-linear association Chi-squared test and will be presented as percentages (%). Receiver operator curve (ROC) analysis will be employed to display the relationship between sensitivity and false positive (FP) rate (1-specificity) and to select the best cut-off value for umbilical cord IL-6 and CRP to predict EOS. Data will be as adjusted by gestational age at delivery, administration of prenatal corticosteroids and antibiotics. Differences will be considered statistically significant at a confidence level of  $p < 0.05$  with two-sided alternative hypotheses

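### IL-6 and CRP cut-offs are chosen by ROC without a stated criterion, and accuracy is then reported in the only cohort with no combination rule, internal validation or confidence interval, so sensitivity will tend to be optimistic

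*Combined protocol and SAP*

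**What the plan says.** Section 14 (Biostatistics) uses ROC curves "to select the best cut-off value for umbilical cord IL-6 and CRP to predict EOS". It does not say what makes a cut-off best, or how tied cut-offs are resolved.

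Section 3, Specific Aim 2, adds: "We will also calculate sensitivity, specificity, negative predictive and positive predictive values of IL-6 and CRP individually". The same sentence extends this to "a combination of IL-6 and CRP in the diagnosis of EOS in VLBW infants", without saying how two results become one. Section 3, Clinical Data Collection, repeats the intention: "We will also find out specificity, sensitivity, positive and negative predictive values of CBC, I/T ratio, blood culture, CRP and IL-6".

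One single-centre cohort is described: "we hope to recruit our desired sample size (n=63) in about 18 months". I found no split sample, cross-validation, bootstrap, external set or confidence interval anywhere in the document. The only inferential statement is the two-sided 0.05 threshold in section 14. Section 2.1 mentions a cord-blood CRP cut-off of 5 mg/dl, but as another study's result and not as a cut-off for this one. No IL-6 cut-off is given.

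**The concern.** A cut-off picked because it separates these infants well will look better in them than in new infants. EOS cases are likely to be the smaller group, and with few of them the chosen cut-off fits their particular values, so sensitivity takes most of the bias. The unstated criterion and the missing combination rule leave further choices open after the data are seen.

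The plan looks beyond the study. Specific Aim 2 says of the marker and antibiotic-duration data: "In future, this may be very useful information in deciding antibiotic duration". Section 13 (Potential Benefits) says that adding these tests "may avoid or prevent unnecessary and prolong antibiotic use in ELBW infants". A reader with that use in mind will look first at missed cases, which is where the figures would be most flattering.

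**Working it through.** **The plan's own figure.** The 63 comes from a correlation of 0.4, alpha 0.05 and power 0.95. The Fisher-z formula n = ((z_alpha + z_power)/atanh(0.4))² + 3 gives, one-sided, ((1.645 + 1.645)/0.4236)² + 3 = 63.3. So 63 is reproduced as a one-sided correlation sample size. It sets no target for EOS cases or for the precision of sensitivity.

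**Inputs for the check.** N = 63 is from section 3, Power analysis. The EOS count k, the AUC and the criterion are not in the documents and are assumptions here.

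**Model.** The marker is normal with unit variance in both groups and is shifted in cases by d = √2·Φ⁻¹(AUC). Candidate cut-offs lie midway between observed values, and ties are broken at random. For a chosen cut-off c, apparent sensitivity is the share of the k cases above c, and true sensitivity is 1 − Φ(c − d). Optimism is the mean of apparent minus true over at least 4,000 simulated cohorts.

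**Which AUC.** Under this model AUC = Φ((z_Se + z_Sp)/√2). The figures cited in sections 2.1 and 2.2 imply:
- preterm cord IL-6, 96%/94%: Φ((1.751 + 1.555)/1.414) = 0.99
- all-infant cord IL-6, 87%/90%: Φ((1.126 + 1.282)/1.414) = 0.96
- cord CRP, 50%/97%: Φ((0 + 1.881)/1.414) = 0.91

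I therefore show 0.8 to 0.99. The cited figures may themselves be optimistic.

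**Sensitivity under Youden.**

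| EOS cases | AUC 0.8, apparent vs true | Optimism, AUC 0.8 | Optimism, AUC 0.9 | Optimism, AUC 0.99 |
|---|---|---|---|---|
| 3 | 90% vs 63% | 27 | 24 | 17 |
| 7 | 83% vs 67% | 16 | 14 | 9 |
| 10 | 81% vs 68% | 13 | 11 | 7 |
| 20 | 78% vs 70% | 8 | 6 | 4 |

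**Other criteria, AUC 0.8.**
- Closest to the corner: about 24, 13 to 14, 10 and 6 points at the same four counts.
- At least 90% observed sensitivity: 100% vs 88% with 7 cases, and 90% vs 86% with 20.
- Best sensitivity subject to at least 90% specificity: this depends on ties. Taking the lowest tied cut-off gives about 2 points or less. Random ties give about 9 points with 3 cases, 5 to 6 with 7 and 2 with 20. Taking the highest gives about 10 with 7.
- Cut-off at the 90th percentile of non-cases: 48.1% vs 48.3% with 7 cases, so no optimism.

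**Predictive values, AUC 0.8, Youden.** With 7 cases, mean sensitivity is 83.0% apparent vs 66.6% true, and specificity 75.8% vs 73.8%.
- PPV apparent: 0.830×7/(0.830×7 + 0.242×56) = 30.0%. True: 0.666×7/(0.666×7 + 0.262×56) = 24.1%.
- NPV apparent: 0.758×56/(0.758×56 + 0.170×7) = 97.3%. True: 0.738×56/(0.738×56 + 0.334×7) = 94.6%.

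The same step gives PPV 15.9% vs 11.2% and NPV 99.3% vs 97.6% with 3 cases, and PPV 59.8% vs 53.7% and NPV 88.3% vs 83.9% with 20.

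**Combination rule.** Take two conditionally independent markers, each 80% sensitive and 80% specific. Either-positive gives sensitivity 1 − 0.2² = 96% and specificity 0.8² = 64%. Both-positive gives 64% and 96%.

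**Precision.** Clopper-Pearson 95% limits are 29-100% for 3/3, 42-100% for 6/7 and 56-94% for 16/20. They treat the cut-off as fixed, so they do not remove the optimism.

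**Leave-one-out, Youden, AUC 0.8.** Average sensitivity against truth is 52% vs 60% with 2 cases, 60% vs 64% with 3, 67% vs 67% with 7 (SD 15 points) and 70% vs 71% with 20.

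**The case against.** The strongest reply is that the IL-6 and CRP work is a research-only sub-study (section 5), that the cited accuracy implies a higher AUC than 0.8, and that imprecision with few cases exceeds the bias. All three are fair. The first limits the weight of the point, although the accuracy estimates are nowhere called exploratory. The second lowers the optimism but does not remove it: at AUC 0.99 it is still 9 points with 7 cases. The third is a reason to report intervals, which the plan also lacks. It is also true that leave-one-out is noisy with 7 cases and uninformative with 2.

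A reader might also infer more than the documents support:
- **That 27 points is the expected bias.** No EOS count, AUC or criterion is given, so no single figure can be attached to this trial.
- **That NPV suffers most when cases are fewest.** At AUC 0.8 with Youden, NPV inflation falls as cases become fewer, and PPV is inflated more than NPV at every count.
- **That any fixed-specificity rule would avoid the problem.** It does so reliably only when the cut-off is set from non-cases alone.
- **That care in this study is at risk.** Section 3 keeps the clinical team blind to the cord-blood sepsis results and does not use IL-6 or CRP clinically.

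That accuracy is estimated in the same infants is itself an inference, but a secure one: no second cohort and no study cut-off is described.

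**Conclusion.** The point holds and should be acted on, as an inexpensive improvement to the analysis plan. Followed as written, with any of the usual criteria, the plan will report sensitivity that is too high on average. Under Youden the illustrative optimism runs from 4 points (20 cases, AUC 0.99) to 27 points (3 cases, AUC 0.8). At AUC 0.8, PPV is inflated by about 5 to 6 points, and NPV by about 2 points with 3 cases, rising to about 4 with 20.

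The direction of the bias is secure for these criteria. Its size rests on an equal-variance binormal marker, 63 infants, and assumed case counts and AUCs. The absence of a criterion, a combination rule, internal validation and confidence intervals is a matter of text and needs no assumption.

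**What to change.** Add the following to section 14, before assay results are linked to EOS status. Section 3 says the tests are run in blocks on stored samples, so there is time.

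1. State the cut-off criterion, including how tied cut-offs are resolved.
2. State the rule for combining IL-6 and CRP: either positive, both positive, or a specified score.
3. Report the AUC with a confidence interval.
4. Report sensitivity, specificity, PPV and NPV at the ROC-chosen cut-off as apparent and hypothesis-generating, with the number of EOS cases and exact 95% intervals. Note that these intervals do not correct the optimism.
5. Beside them, report leave-one-out sensitivity and specificity, re-choosing the cut-off each time. Note that this is uninformative with very few cases.

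The cost is a few lines of text, a short script and less favourable reported accuracy. No new samples or infants are needed.

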### *2.4 Reducing blood withdrawals in preterm infants*

Placental/umbilical cord blood (PUCB) could be used in the evaluation of EOS in PI. (23,26). Christensen found reduced iatrogenic blood loss using PUCB sample during the first day of life ( $p < 0.007$ ), and for the first week of life ( $p < 0.001$ ) in contrast with infant blood sample controls (23). This postpone or eliminating blood transfusion in the VLBW preterm infant (23,26).

PUCB for blood cultures could be a convenient alternative to ensure an adequate volume of blood (24). Meena et al. compared PUCB with blood from infants, (n=40) in the evaluation of sepsis. They found PUCB showed 100% sensitivity and 95% of specificity compared with 100% of sensitivity and 74% of specificity using blood from infants. Beeram et al found that the utilization of umbilical blood samples for CBC and blood cultures are a reliable alternative for sepsis workup in neonates (25).

In the current study, we want to find out the efficacy of PUCB in the evaluation of EOS in preterm infants compared to blood collected from the infant (24).

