#### *Placenta/Umbilical Cord blood (PUCB):*

In the current research project, we want to use PUCB to do sepsis evaluation in VLBW infants. There is approximately 15 – 20 mL/kg blood in the placenta and umbilical cord. That means in VLBW infants (<34 w) there will be approximately 15 – 20 mL blood in the placenta and umbilical cord which is fetal blood hence it can be utilized to do EOS sepsis evaluation. This

will save blood in VLBW infants. As blood in PUCB is nothing but fetal blood. There is a misconception that fetal and maternal blood is mixed in the placenta. Actually, there is no mixing of maternal and fetal blood in the placenta. After birth, the placenta and umbilical cord are discarded along with the blood inside. We want to utilize fetal blood in the placenta/umbilical cord for the evaluation of EOS in VLBW infants.

The current research project will evaluate the utility of PUCB to assess early onset sepsis (EOS) in VLBW infants (<34 weeks). This study will not affect the management of the infants at all. The lab tests will be done in blocks and hence the results will not be available in real time. The clinical management of infants will be decided by the neonatal team taking care of the infants. The neonatologists will continue to treat infants as per the NICU protocol.

We will compare blood culture, CBC, and I/T ratio results from the infant and PUCB. We will calculate the sensitivity, specificity, positive and negative predictive value of these tests in the evaluation of EOS.

During hospital stay, all VLBW infants get CBC done immediately after birth. After CBC is done, the left-over sample is stored in the hematology laboratory for 24 hours. After 24 hours, this blood sample is discarded. We will collect left over blood from the hematology laboratory to extract serum by centrifuging the blood sample. The serum will be stored at -80°C for future measurements of CRP and IL-6. We will also compare CRP and IL-6 levels in placenta/umbilical cord blood and discarded infant blood. Additionally, we will evaluate the role of adding IL-6 and CRP in the evaluation of EOS in VLBW infants.

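### ROC analysis is specified for cord IL-6 and CRP only, so for these markers the plan has no analysis of whether cord blood identifies EOS as well as infant blood

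*Combined protocol and SAP*

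**What the plan says.** The objective in section 3 (Concise Summary of Project) is "To compare placental/umbilical cord blood and blood from the infant in the evaluation of EOS in VLBW infants". Section 2.4 puts the same question: "we want to find out the efficacy of PUCB in the evaluation of EOS in preterm infants compared to blood collected from the infant".

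For IL-6 and CRP, section 3 provides for measurement in cord blood and in serum from the infant's leftover CBC sample. The summary says only that the two will be compared. The subsection on placenta/umbilical cord blood is more specific: "We will also compare CRP and IL-6 levels in placenta/umbilical cord blood and discarded infant blood". Section 14 then names ROC analysis for one source only, "to select the best cut-off value for umbilical cord IL-6 and CRP to predict EOS".

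For the routine tests, the same subsection of section 3 says "We will compare blood culture, CBC, and I/T ratio results from the infant and PUCB" and then "We will calculate the sensitivity, specificity, positive and negative predictive value of these tests in the evaluation of EOS". The Clinical Data Collection subsection extends this to every marker: "We will also find out specificity, sensitivity, positive and negative predictive values of CBC, I/T ratio, blood culture, CRP and IL-6". It gives neither the blood source nor the cut-off.

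No section names a paired comparison of AUC, sensitivity or specificity, an agreement statistic or a margin. The tests named in section 14 are Mann-Whitney and the linear-by-linear chi-squared test. Neither compares the accuracy of two specimens from the same infant.

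**The concern.** The question is comparative and concerns diagnosis, but the one detailed accuracy analysis covers a single source. Comparing levels does not fill the gap. A constant difference between cord and infant levels leaves the AUC unchanged, so shifted levels can go with equal discrimination. Equal average levels can also hide unequal discrimination. Either result could be misread as evidence about cord blood's usefulness.

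There is a second risk. Sensitivity and specificity are promised for IL-6 and CRP without a stated source. If they were reported for infant blood, the only cut-off that the plan generates is the one optimised on cord blood in the same infants. Cord would then be judged at its own best threshold and infant blood at a borrowed one. That tilt favours the study hypothesis.

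The protocol's own background makes a level difference plausible. It describes IL-6 peaking at 2 to 3 hours and returning to baseline by 6 to 8 hours, and CRP rising 6 to 18 hours after a stimulus. Cord blood is taken at delivery into a heparinized container. Infant serum comes from a CBC remnant that the laboratory keeps for 24 hours.

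**Working it through.** **1. The plan's own figure.** Section 3 (Power analysis) gives n = 63 for r = 0.4, alpha 0.05 and power 0.95. By Fisher's z, N = ((z_alpha + z_power)/atanh(r))² + 3.
- One-sided: ((1.645 + 1.645)/0.4236)² + 3 = 63.3. The exact test gives 63, so the figure reproduces.
- Two-sided, as section 14 requires: ((1.960 + 1.645)/0.4236)² + 3 = 75.4. The exact test gives 75.

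For this point, what matters is that 63 was sized for a correlation and not for a difference in accuracy between sources.

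**2. What is planned, by marker.**

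| Marker | Between-source comparison stated | Accuracy measures stated | ROC and cut-off | Paired accuracy comparison |
|---|---|---|---|---|
| Culture | results | yes | not needed | none |
| CBC, I/T | results | yes | none | none |
| IL-6, CRP | levels | yes, source not stated | cord only | none |

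**3. Number of EOS cases (assumption).** The documents give no EOS rate for this cohort. At an assumed 5% or 10%, 63 infants yield 63 × 0.05 = 3.2 or 63 × 0.10 = 6.3 cases. Hence the range of 3 to 7.

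**4. Effect of a borrowed cut-off (simulation; every input except n = 63 is assumed).** Both sources have the same true discrimination (1.5 SD separation) and a within-infant correlation of 0.7. The Youden cut-off is chosen on cord blood and applied to both. The entries are cord minus infant in (sensitivity + specificity):

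| Infant level shift | 3 cases | 5 cases | 7 cases |
|---|---|---|---|
| none | 0.25 | 0.18 | 0.15 |
| 0.5 SD lower | 0.35 | 0.27 | 0.23 |
| 0.5 SD higher | 0.23 | 0.19 | 0.18 |
| own cut-off in each source | at most 0.01 | at most 0.01 | at most 0.01 |

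A separate simulation (AUC 0.8 in both sources, correlation 0.6, 6 cases, no shift) shows the same pattern. Sensitivity is 0.84 for cord against 0.67 for infant blood at the cord cut-off, and 0.84 against 0.84 with own cut-offs.

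**5. How much is due to the shift itself.** Remove the in-sample optimism by fixing the cut-off at its true optimum, 0.75 SD.
- No shift: sensitivity = specificity = Phi(0.75) = 0.773, sum 1.546.
- Infant levels 0.5 SD lower: sensitivity Phi(0.25) = 0.599, specificity Phi(1.25) = 0.894, sum 1.493.

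Sensitivity falls from 77% to 60% while specificity rises from 77% to 89%. The net loss is 1.546 − 1.493 = 0.05. Most of the gaps in step 4 therefore come from choosing the cut-off on a handful of cord cases.

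**6. What a paired AUC difference could show.** In the separate simulation (AUC 0.8, correlation 0.6), the SD of the AUC difference is 0.125, 0.089 and 0.071 with 3, 6 and 10 cases. Approximate 95% half-widths are 1.96 × SD = 0.25, 0.17 and 0.14.

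**The case against.** The strongest reply is that a comparison of sources with accuracy measures is already planned. For culture, CBC and I/T ratio that is so, and it stands. A reader might infer that cord and infant blood are never compared for EOS. The documents do not support this, since section 3 compares results from both sources and promises sensitivity, specificity and predictive values. What is missing is a specified paired comparison and, for IL-6 and CRP, any infant-blood ROC.

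A reader might also infer that every side-by-side sensitivity will use a cut-off tuned to cord. That is not supported either. Culture is positive or negative, no ROC cut-off is planned for CBC or I/T ratio, and nothing says that the cord threshold will be applied to infant IL-6 or CRP. A published cut-off is another route. Infant-blood sensitivity for these markers may never be reported, and then the bias in step 4 does not arise. In that case, however, the objective goes unanswered for these markers.

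Finally, the simulated gaps rest on assumptions, and the largest come from one direction of shift. Quoting the fall in sensitivity without the rise in specificity would exaggerate the effect. Both points are fair, so both directions and both measures are shown.

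**Conclusion.** The concern holds in a limited form. For IL-6 and CRP, the written plan specifies ROC for cord blood only and compares the sources on levels, so it contains no analysis that answers the comparative accuracy question. For culture, CBC and I/T ratio, accuracy will be described but no paired comparison is specified. This conclusion comes from the text and needs no simulation.

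The borrowed cut-off is a conditional risk, not a planned step. Under the assumed inputs it would give cord blood a spurious lead of about 0.15 to 0.25 in sensitivity plus specificity with no shift, 0.23 to 0.35 with infant levels 0.5 SD lower, and 0.18 to 0.23 with them 0.5 SD higher. With own cut-offs the lead is at most 0.01. Those sizes depend on the assumed separation, correlation and number of EOS cases, none of which the documents give. The level shift alone accounts for about 0.05.

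**What to change.** In section 14:
- Run the same ROC analysis for IL-6 and CRP, and for WBC, band count and I/T ratio, in both cord and infant blood.
- For infants with both results, report the paired AUC difference (cord minus infant) with a 95% CI, by DeLong or bootstrap. Present it as an estimate, not as a significance test.
- State that a cord-derived cut-off will not be used to judge infant blood.
- Describe any source-specific cut-off as exploratory. Validating separate cut-offs is not credible with so few cases.

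The cost is revised wording and a few more analyses of values that the study already plans to obtain. No further samples are needed. The drawback is imprecision: with few EOS cases the interval for the AUC difference will be wide, as step 6 shows. That reflects what a cohort of this size can support.

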## **2. Background:**

Early and timely diagnosis of EOS is very important but challenging at the same time as clinical signs are nonspecific. Routine Laboratory tests such as complete white blood count (WBC) with differential count and immature/total neutrophil (I/T) ratio are routinely used to assist in the diagnosis of sepsis in neonates; however, multiple studies have determined that the WBC and immature-to-total neutrophil (I/T) ratio have low sensitivities and specificities (7). The I/T ratio has been found elevated in a quarter to half of the presumptively in infants without sepsis (8,9) with low positive predictive values (7). Consequently, just CBC indices in the evaluation of EOS in neonates is not very helpful, hence use of empiric antibiotic therapy is used in a large number of neonates with clinical suspicion of EOS (8,9).

The “Gold Standard,” blood cultures are not always positive because of low blood volumes are often put in the blood culture bottles and prenatal administration of antibiotics (6, 27). Using biomarkers of sepsis to distinguish septic from non-septic neonates may allow judicious discontinuation of antibiotics, consequently preventing prolonged use of antibiotics and avoiding the appearance of antibiotic-resistant bacteria. Besides, appearance of antibiotic-resistant bacteria, prolonged empiric antibiotic use has been associated with increased risk of necrotizing enterocolitis (NEC), late onset sepsis (LOS), and even increased mortality (10).

Recent studies have shown improved sensitivity and negative predictive value (NPV) of various biomarkers of sepsis compared to CBC indices (11,12). Acute phase proteins, components of the complement system, chemokines, cytokines, adhesion molecules, and cell surface markers have all been investigated as biomarkers of neonatal sepsis (12). The most widely studied and most promising markers include C-reactive protein (CRP), interleukin-6 (IL-6), interleukin-8 (IL-8), procalcitonin (PCT), and tumor-necrosis-factor-alpha (TNF-alpha).

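### Aim 1 asks whether cord blood can replace infant blood, but the plan has no agreement analysis and no acceptance limit; its only inferential criterion is a two-sided difference test at p < 0.05

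*Combined protocol and SAP*

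**What the plan says.** Section 3 (Concise Summary of Project) states the hypothesis: "Placental/umbilical cord blood can be used to do early onset sepsis evaluation in low birth weight infants". Specific Aim 1 compares the two blood sources, "especially comparing white cell count, band count, I/T ratio and if the blood culture is positive or negative", and checks whether the organism is the same when a culture is positive. The PUCB subsection of section 3 repeats the intention: "We will compare blood culture, CBC, and I/T ratio results from the infant and PUCB". It adds that sensitivity, specificity and predictive values will be calculated. The Clinical Data Collection subsection says the data will serve to assess the accuracy of PUCB samples.

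Section 14 (Biostatistics) is the whole of the analysis plan. On continuous data it says: "Demographic and clinical characteristics will be compared using the non-parametric Mann-Whitney U test". Categorical variables get a linear-by-linear chi-squared test. ROC analysis is used to choose cord IL-6 and CRP cut-offs, which belongs to Aim 2. The inferential criterion is: "Differences will be considered statistically significant at a confidence level of" p < 0.05, "with two-sided alternative hypotheses".

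Nowhere do the documents give a paired method, limits of agreement, a kappa or intraclass correlation, an equivalence margin, or a minimum acceptable concordance, sensitivity or specificity.

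**The concern.** Aim 1 is a within-infant substitution question: are the two specimens close enough that one may stand in for the other? A difference test answers another question. A non-significant result can mean that the specimens agree, or that the data are too few or too variable to show that they do not. A significant result can reflect a shift too small to matter. Without a stated limit on how close is close enough, neither result settles whether PUCB can be used.

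Changing to a paired test would respect the design but would not cure this, because the limit would still be missing. The same holds for the accuracy measures: without targets, whether a given sensitivity is good enough would be decided after the data are seen. What is at stake is the study's main conclusion.

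**Working it through.** **The plan's own figure.** Section 3 (Power analysis) gives r = 0.4, alpha 0.05 and power 0.95, yielding 63. By Fisher's z, one-sided: ((1.645 + 1.645) / atanh 0.4)² + 3 = (3.290 / 0.4236)² + 3 = 63.3, or 64. The exact bivariate-normal calculation, one-sided, gives 63. So the figure reproduces, as a one-sided test that a correlation is not zero. The exact two-sided figure is 75, although section 14 specifies two-sided testing. The effect size comes from correlations of CRP with other biomarkers. It says nothing about agreement between two blood sources, and a non-zero correlation would not show agreement.

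**What a difference test can miss.** The documents give no SD, so shifts are in SDs of the within-infant difference. They name no paired test, so a two-sided paired t-test at 0.05 is used as an approximation. With n = 63, √63 = 7.937 and the critical value t(0.975, 62) = 1.999. The noncentrality is shift × 7.937. The miss rates below are from the noncentral t distribution.

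| True shift | Noncentrality | Probability of p > 0.05 |
|---|---|---|
| 0.2 SD | 1.587 | 65% |
| 0.3 SD | 2.381 | 35% |
| 0.5 SD | 3.969 | 2.6% |

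The effect of noise is direct. If the 0.5 SD shift stays fixed in raw units and the SD doubles, it becomes a 0.25 SD shift and the miss rate rises from 2.6% to 50%.

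An independent-sample analysis at 63 versus 63, with shifts now in SDs of a single measurement, misses a 0.3 SD shift 61% of the time: 0.3 × √(63/2) = 1.684, and Φ(1.960 − 1.684) = 0.61.

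**Culture, with assumed counts.** Suppose 3 of 63 infant cultures are positive and PUCB is negative in all 63. The linear-by-linear statistic is (N − 1)r² with N = 126.
- r² = (3×63 − 60×0)² / (63×63×3×123) = 0.0244.
- 125 × 0.0244 = 3.05, so p = 0.081.
- The exact McNemar test gives 2 × 0.5³ = 0.25. At least 6 discordant pairs, all in one direction, are needed for p < 0.05 (2 × 0.5⁶ = 0.031).
- Overall concordance is 60/63 = 95% (exact 95% CI 87% to 99%), while sensitivity is 0/3.

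So neither a difference test nor overall concordance would expose a specimen that missed every infection.

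**What an acceptance rule can deliver at 63 pairs.** The 95% CI half-width for a mean difference is 1.999 / 7.937 = 0.25 SD. Assume a true difference of zero and 80% power.
- Two one-sided 5% tests (a 90% CI inside the limits): t(0.95, 62) = 1.670, and (1.670 + 1.282) / 7.937 = 0.37 SD.
- The stricter rule of a 95% CI inside the limits: (1.999 + 1.282) / 7.937 = 0.41 SD.

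Under the two one-sided 5% tests, power at 63 pairs is 52% for a limit of 0.3 SD, 86.5% for 0.4 SD and 98% for 0.5 SD. Here more noise or fewer pairs makes a positive conclusion harder to reach.

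**The case against.** A reader might infer that the plan will treat p > 0.05 as support, so that noisy or missing data work in favour of the hypothesis. The documents do not say so. The sentence in section 14 is a general significance convention. The Mann-Whitney test is assigned to demographic and clinical characteristics, the chi-squared test to unspecified categorical variables, and neither to the comparison of PUCB with infant blood. This stands. What remains is that Aim 1 has no assigned analysis and no acceptance criterion.

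Nor do the documents show that pairs will be lost from the 63. Section 9 already counts after-hours births within the 50–60% recruitment rate, and 80 × 1.5 × 0.5 to 80 × 1.5 × 0.6 gives 60 to 72 infants in 18 months.

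Other evidence is planned: sensitivity, specificity, predictive values and the same-organism check. None of these is built to improve as data get noisier. That is fair, but none has a target.

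PUCB might also differ legitimately by being better. Section 2.4 cites a study with specificity of 95% in cord blood against 74% in infant blood, and sections 1 and 2 describe culture as insensitive when the sample volume is low. This too stands: a PUCB-only positive culture should not automatically count as a PUCB failure.

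Finally, Aim 1 openly compares components. A single per-infant concordance measure as the deciding variable is not called for by the documents. It would need reading thresholds that they do not state, and it would be dominated by negatives.

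**Conclusion.** The concern holds as a gap in the plan. Aim 1 asks a substitution question, but the only inferential criterion is a difference test, the named tests are unpaired, and no agreement analysis, acceptance limit or accuracy target is given. A conclusion that PUCB can be used could not validly follow from the stated inference.

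The sizes are illustrative. The 35% miss rate at 0.3 SD assumes 63 complete pairs and a paired-t approximation, and the p = 0.081 culture example assumes 3 positives. The gap itself does not depend on those assumptions. The documents do not support saying that the investigators intend to read non-significance as success. The study is observational, with clinicians blinded to PUCB results, so the issue bears on the conclusion and not on the care of enrolled infants.

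**What to change.** For the PUCB-versus-infant comparisons in section 14, replace the p < 0.05 criterion with paired estimation.

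- **WBC, band count and I/T ratio:** report the within-infant difference with a 95% CI, and limits of agreement, since a mean difference near zero can hide wide scatter between individuals. Before any PUCB result is seen, the investigators fix acceptable limits in the units of each measurement. Conclude that PUCB can be used only if the CI lies inside them; otherwise report that it differs or that the result is inconclusive.
- **Culture:** report positive and negative agreement separately with exact CIs. List every discordant pair in both directions, without presuming that a PUCB-only positive is an error. Draw no substitutability conclusion if positives are too few.
- **Wording:** state that p > 0.05 is not evidence of interchangeability.
- **Per-infant overall concordance:** optional, as a descriptive secondary summary only.

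The cost is protocol and analysis-plan wording, plus the work of agreeing the limits; no extra blood or enrolment is requested. The downside is a real chance of an inconclusive result. With 63 pairs and no true difference, 80% power is available only for limits of about 0.37 SD or wider if a 90% CI decides, or about 0.41 SD if the 95% CI decides. The plan should state which interval decides.
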